### 3.4 Study duration for subjects and stopping rules

The study duration is of 9 months for subjects, from index visit to end of follow-up. Study ends with routine consultation at GP's office 6 to 9 months after index visit or, if no consultation is scheduled, with telephonic interview at 9 months.

Intermediate analysis is done at 3 months and *stopping rules* are:

- The CPR is so effective that it has to be applied to control group
- There is no significant difference between intervention and control group or no data indicating that a difference may be expected at the end of complete follow-up
- Non use of the CPR by GPs of the intervention group
- Unexpected unfavourable effect on patients

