### 3.2 Endpoints

In order to assess implementation and effectiveness of the cardiovascular CPR (targeted at GPs) on the management of chest pain and patient's outcome, we will measure:

- Hospitalizations, severe CHD at 9 months among patients included
- Number and type of extra investigations and referrals run by GPs to manage patient's chest pain
- Use/non use of the CPR by GPs, acceptability and satisfaction

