## 6. Evaluation criteria

Aiming to assess both implementation of the cardiovascular CPR and its potential effect on chest pain management, evaluation criteria are split in two classes. On one hand, criteria concerning use of the CPR, evaluated by few questions in de CRF directly addressed to GPs. On the other hand, criteria aiming to measure impact of the CPR on chest pain management and patient's outcome. These are to be filled in by GPs for each patient complaining of chest pain at the time of the index visit (CRF) and at the end of follow-up (6 to 9 months), and by research team for intermediate analysis.

Implementation:	
Acceptability of the CPR	
 
- Use/non use of the CPR
 
- Reassurance with low-risk result
 

Satisfaction	
 
- Discrete visual analogue scale
 

Impact:	
Extra investigations of chest pain	
 
- None
 
- ECG
 
- Thoracic radiography
 
- Laboratory (CRP, FSC, CK, D-dimers, Troponines, BNP)
 
- Cardiac stress test
 
- Others (precise)
 

Referral	
 
- None
 
- Hospital / emergency setting
 
- Cardiologist (less than 6 hours, less than one week, more than one week, telephonic interview)
 
- New consultation
 
- Other (precise)
 

Patient's outcome at 9 months	
 
- Hospitalisation(s) during follow-up
 
- CHD / no CHD, with degree of certainty (discrete visual analogue scale)
 

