## **9. Quality control and assurance**

### **9.1 Monitoring**

Follow-up will last 6 to 9 months, with intermediate analysis at 3 months. To insure the data collection and avoid loss of follow-up, a member of research team will phone patients at 3 months and will also contact GPs at 9 months to insure closing of the follow-up.

*Quality control* will be provided by an independent GP and a hospital internist not aware of the current study. They will both review 20% of the cases, randomly

selected, to insure correct management of patients and validity of the data collected before analysis. Both reviewing and follow up should certify as surely as possible and without any invasive procedure the correct diagnosis and management of patients' complaint.

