### 10.1 Number of subjects

Calculation of the number of subjects is based upon the TOPIC study, targeting the same population of patients with chest pain. We used a sample size calculation table for cluster-randomized trial to calculate the number of clusters needed with different values of subjects per cluster ( $m$  value). Calculation has been made for different variables up to the endpoints of the study. We chose the following variables for the calculation of the number of subjects: number of paraclinical tests, number of referral to specialist, number of hospitalisations.

[figure not shown]
All the true proportions for each variable in the control arm of the sample size calculation table come from the TOPIC study results. We then decided a reasonable decrease expected in the rate of paraclinical tests, referral and hospitalisations while using the CPR, which led us to the expected proportions in the intervention arm

In the TOPIC study, investigators reported 42% (284/672) of patients with paraclinical tests, 16% (110/672) with referral to specialist and 8% (53/672) hospitalised up to 12 months of follow-up (2).

To choose the number of cluster needed in each arm of the trial we took a coefficient of variation of 0.2. Final decision about number of subjects per cluster and number of clusters was based upon practical considerations so that recruitment procedure remains comfortable for GPs and to limit its duration.

Based upon the results shown above, we chose a number of 150 GPs in each arm, with 50 patients per cluster, so that the power of the study is sufficient to get a difference in paraclinical tests. We therefore need a total amount of 300 GPs, each of them recruiting 50 patients complaining of chest pain, leading us to a total amount of 15,000 patients.

Duration of inclusion is also calculated upon the TOPIC study in which chest pain occurred in 672 cases among 24,620 consultations during 300 weeks. We can therefore expect 2 to 3 patients with chest pain per week on the average, which leads us to an inclusion period of about 6 months for GPs to enrol the 50 patients needed.

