### **Hospitalisations en lien avec la douleur thoracique durant la période de suivi :**

oui  / non

*Si oui*, durée : \_\_\_\_ jour(s)

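### The outcome is labelled 9 months, but follow-up may close at any routine visit from month 6 and no event dates are collected, so observation time is unequal and only partly repairable

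*Protocol*

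**What the plan says.** Section 3.4 first fixes the period: "The study duration is of 9 months for subjects, from index visit to end of follow-up". It then says that follow-up ends with a routine consultation "6 to 9 months after index visit or, if no consultation is scheduled, with telephonic interview at 9 months".

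The other sections divide between the two horizons.

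- **Nine months:** section 3.2 lists "Hospitalizations, severe CHD at 9 months among patients included"; the outcome row in section 6 is headed "Patient's outcome at 9 months"; the Annex 3 form is titled for 3 and 9 months.
- **Six to nine months:** section 6 has GPs record outcome "at the end of follow-up (6 to 9 months), and by research team for intermediate analysis"; section 9.1 states "Follow-up will last 6 to 9 months, with intermediate analysis at 3 months"; section 7.2 ties return of the final questionnaire to the same window.
- **In between:** the Synopsis gives nine months as a maximum. Section 3.1 has GPs follow patients to nine months by phone or ordinary consultation.

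Section 9.1 also has research staff contact GPs at 9 months to close follow-up.

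Annex 3 asks for cumulative numbers of tests and specialist visits, a yes/no item for "Hospitalisations en lien avec la douleur thoracique durant la période de suivi" with length of stay, and CHD yes/no. The form carries its own completion date but no dates of events. For planning, section 10.1 uses a third horizon: "8% (53/672) hospitalised up to 12 months of follow-up".

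**The concern.** A cumulative outcome has meaning only with its time window. Here the window is 9 months for a patient with no scheduled consultation and as little as 6 months for a patient who has one. A reading taken at month 6 would be filed on the form as the 9-month result.

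Having a consultation scheduled is unlikely to be random. It plausibly goes with illness, so the patients who lose late events may be those most likely to have them. It may also differ by arm: section 6 counts reassurance after a low-risk score as an implementation criterion and a new consultation as an impact criterion, and section 8.1 expects minor changes in GP behaviour. The link to arm is an inference; the protocol does not say that the CPR alters routine visits half a year later.

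The outcomes at stake are late hospitalisation, CHD status, and follow-up tests and referrals. They carry the part of the second objective that says patient outcome is not compromised. Because event dates are not collected, the gap cannot be fully closed at the analysis stage.

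**Working it through.** **Plan's own figures.** 2 × 150 GPs × 50 patients = 15,000, as stated in section 10.1. 53/672 = 7.89%, which the protocol rounds to 8%.

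**Hospitalisation by reading time.** Assume a constant rate: F(t) = 1 − exp(−λt), with λ = −ln(1 − 53/672)/12 = 0.00685 per month.

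| Reading at | Cumulative hospitalisation | Share of 9-month events missed |
|---|---|---|
| 6 months | 4.02% | 1 − 4.02/5.98 = 33% |
| 7.5 months | 5.00% | 1 − 5.00/5.98 = 16% |
| 9 months | 5.98% | 0 |

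Using the rounded 8% instead gives 4.1% at 6 months and 6.1% at 9.

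**False arm difference with no true effect.** If shares v₀ (control) and v₁ (CPR) are closed at an early visit at time t, the difference is (v₀ − v₁) × [F(9) − F(t)]. The shares are assumptions; the protocol gives none.

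| Closed early, control v CPR | Visits at 7.5 months | Visits at 6 months |
|---|---|---|
| 50% v 40% | 0.10 points | 0.20 points |
| 60% v 40% | 0.19 points (5.39% v 5.59%) | 0.39 points |
| 80% v 40% | 0.39 points | 0.78 points |
| 100% v 0% (limit) | 0.97 points | 1.95 points |

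If half of the 12-month events fall in the first month and the rest are spread evenly, 60% v 40% gives 0.11 points (visits at 7.5 months) or 0.22 (at 6 months), and the limit at 6 months is 1.08.

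**Scale.** The text of section 10.1 gives no significance level or power, so a two-sided 5% level and 80% power are assumed. The usual formula for an unmatched cluster trial is

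c = 1 + (1.96 + 0.84)² × {[p₀(1 − p₀) + p₁(1 − p₁)]/m + k²(p₀² + p₁²)}/(p₀ − p₁)²,

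with c = 150, m = 50 and k = 0.2 from section 10.1. Solving for p₁:

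- p₀ = 7.89% gives p₁ = 6.61%, a detectable difference of 1.28 points.
- p₀ = 5.98% gives p₁ = 4.88%, a detectable difference of 1.10 points.

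**Direction.** In every row the arm with fewer early closures shows more events. If CPR patients have fewer scheduled visits, the artefact adds events to the CPR arm.

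**The case against.** Several points on the other side stand.

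- The Annex 3 form is also completed by research staff at 3 months for every agreeing patient, so one common cut across arms exists.
- The form has a completion date, so each patient's length of observation can be derived, and an analysis plan not shown here may use it.
- Section 3.1 speaks of follow-up until nine months, and section 9.1 has a 9-month contact with GPs.
- Tests and onward management at the index visit are recorded that day and cannot be touched by the window. Section 10.1 justifies the sample size by paraclinical tests, not hospitalisation.
- The trigger is a scheduled routine consultation, not a return for chest pain, so an effect of the CPR on it is uncertain.

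These points limit the size of the problem but do not remove it. The 3-month cut is not the 9-month endpoint. The completion date gives exposure but does not place events within it, so adjusting by exposure alone needs a constant-rate assumption. Sections 3.1 and 9.1 do not describe a repeat reading for a patient already closed at a visit.

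A reader might infer that the arm comparison is biased by about two points, more than the trial can detect. That needs every patient in one arm read at month 6 and every patient in the other at month 9, and nothing in the protocol suggests such a split. A reader might also infer that the rule would manufacture a favourable result for the CPR. With CPR patients observed longer, it would do the reverse.

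**Conclusion.** The conflict between a 9-month outcome and a 6-to-9-month reading is explicit in the protocol and holds whatever the split of visits between arms. Observation time varies by up to a third. Under a constant rate, about a third of 9-month hospitalisations are missed in a patient read at month 6; the loss is smaller if events cluster early.

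Bias between arms is possible but not established. For assumed moderate imbalances it is about 0.1 to 0.4 points, against about 1.1 to 1.3 detectable. Only large imbalances with visits near month 6 come close to the detectable difference. Only hospitalisation was quantified; the size of any effect on CHD status or on follow-up tests and referrals cannot be derived from the protocol.

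This should be corrected before enrolment, because missing event dates cannot reliably be recovered later. It does not undermine the design or the sample size.

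**What to change.** 1. **One horizon.** Reconcile the Synopsis, sections 3.1, 3.2, 3.4, 6, 7.2 and 9.1, and the Annex 3 title on a single 9-month outcome. A visit between 6 and 9 months may supply data but should be described as a last contact, not as the 9-month reading.
2. **Event dates.** Add to Annex 3 the dates of hospitalisation, referral, investigation and CHD diagnosis. Use the form's existing date as the date of last contact.
3. **Analysis.** Analyse to 9 months by time at risk, censoring earlier last contacts. Censoring handles unequal length but assumes that early closure is unrelated to prognosis, which is why item 4 helps.
4. **Update where feasible.** Use the 9-month staff contact with GPs already planned in section 9.1 to update patients read earlier. This has to go through the GP, because section 7.2 deletes mobile numbers after the intermediate analysis.
5. **Section 10.1.** State that the 8% covers up to 12 months and give the assumed 9-month rate, about 6% under a constant rate. The protocol does not report a 9-month proportion from TOPIC. The sample size need not change.

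The cost is protocol wording, some date fields on one form and some added form work for GPs. A compulsory 9-month call to every patient seen early would cost much more. If, say, 70% of controls and 50% of CPR patients were seen early, it would mean 0.7 × 7,500 + 0.5 × 7,500 = 9,000 calls, or 30 per GP. It is therefore not the main proposal.

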### 3.1 Overall description

This trial aims to assess implementation of a new cardiovascular CPR in primary health care. It is built as a prospective cohort study of primary care patients with chest pain. The cluster randomized trial design allows us to randomize GP's offices in two groups, one using the CPR in daily practice and the other working without, according to usual care practice. Thus, randomization and intervention are targeted at the level of GP's offices. Patient's outcome however is measured at the individual's level thanks to a case report form (CRF). Use of the CPR is measured directly by a few questions intended for GPs.

GPs selected to use the cardiovascular CPR will get intensive training to make as sure as possible that they use it in an equivalent way (see Annex 1 for description of GPs training). GPs of the usual practice group should not be aware of the CPR and will not get any information about it. In both groups, GPs will have to fill in a CRF for each patient complaining of chest pain.

Follow-up ends nine months after patient's index visit. An intermediate analysis is planned at three months. Members of research staff are designed to make sure that case report forms are complete for each patient and will get in touch with every agreeing patient at three months (intermediate analysis). GPs will assure the follow up until nine months (end of follow up) either by telephonic interviews or usual consultation. The research staff will control the follow up and remember GPs if necessary.

Independent physicians will review a defined randomized number of cases. They will control patient's condition at the end of the follow-up, validate the correct management of patients and verify the validity of the initial diagnosis of cardiogenic chest pain.

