#### 4.4 Selection and recruitment procedure

Swiss GPs and physicians of the Department of Ambulatory Care and Community Medicine in Lausanne will be contacted and asked to participate the study. Starting from a defined date, each GP will enrol a defined number of patients reporting any type of chest pain, according to inclusion criteria.

Sampling of all the GPs recruited will be performed in order to assess characteristics of participants (age, place, type of practice) and minimize cohort effect. Investigators may decide to use pre-existing GPs network such as Sentinella, which can insure correct sampling of Swiss GPs.

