### **8.2 Monitoring of adverse events**

Intermediate analysis is done at 3 months after patients index visit to display any unexpected effect of the CPR. In case of unfavourable effect for patients included, study will be immediately stopped. For stopping rules, please refer to *Chapter 3.4*.

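### The 3-month stopping rule lets a non-significant interim result end the trial by itself, names no endpoint, and relies on data that arrive largely as or after enrolment closes

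*Protocol*

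**What the plan says.** Section 3.4 gives four stopping rules for the intermediate analysis at 3 months. The second is "There is no significant difference between intervention and control group or no data indicating that a difference may be expected" once follow-up is complete. The first is "The CPR is so effective that it has to be applied to control group". The other two are non-use of the score by intervention GPs and an unexpected unfavourable effect on patients. None names an endpoint or an amount of data.

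On timing, section 8.2 states: "Intermediate analysis is done at 3 months after patients index visit to display any unexpected effect of the CPR". It adds: "In case of unfavourable effect for patients included, study will be immediately stopped". Section 3.1 says that research staff "will get in touch with every agreeing patient at three months (intermediate analysis"). Section 4.4 says: "Starting from a defined date, each GP will enrol a defined number of patients". Section 10.1 takes a rate from the TOPIC study, "672 cases among 24,620 consultations during 300 weeks", "which leads us to an inclusion period of about 6 months for GPs to enrol the 50 patients needed".

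The score is calculated at the index visit, before the GP decides on tests (section 3.5 and Annex 1). Control GPs do not use it; the investigators calculate it afterwards for their patients. Section 2 aims to spare investigations without worse management or outcome. Section 3.2 places hospitalisation and severe CHD at 9 months. Section 10.1 sizes the trial on paraclinical tests.

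**The concern.** The second rule joins two different ideas. Having no prospect of a difference at the end is a futility criterion. Having no significant difference at an early look is not: a well-designed trial with a real effect often fails to reach significance on partial data. Because the two are joined by *or*, the weaker condition is enough to stop.

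As no endpoint is named, the rule can also be read onto patient outcome. There, similarity between the arms is the wanted result, and stopping on it would cut off the 9-month data needed to support the claim of no harm.

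The second issue is timing. The intervention happens once per patient, at the index visit. If 3-month data accumulate mainly when enrolment is ending or over, neither stopping at once nor giving the score to the control group can change how any enrolled patient is assessed.

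**Working it through.** **Inputs from the protocol (section 10.1).** 150 GPs per arm, m = 50 patients per GP, coefficient of variation k = 0.2, control proportion 42% with paraclinical tests (284/672), inclusion of about 6 months.

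**Assumed, because the sample-size table is not readable.** Two-sided 5%, power 80% or 90%, intervention proportion 38%.

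**1. The plan's own figures.** 2 × 150 × 50 = 15,000, as stated. 672/300 = 2.24 patients per week, so 50/2.24 = 22.3 weeks (5.1 months). At 2 to 3 per week the period is 5.8 to 3.8 months, so about 6 months is the upper end. The 150 GPs cannot be reproduced from the readable text, but the assumed effect is compatible with it:

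- V(m) = [p0(1−p0) + p1(1−p1)]/m + k²(p0² + p1²)
- V(50) = 0.4792/50 + 0.04 × 0.3208 = 0.00958 + 0.01283 = 0.02242
- c = 1 + (1.960 + 1.282)² × 0.02242/0.04² = 148.2, i.e. 149 GPs per arm at 90% power

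An 80% power design with 150 GPs corresponds to about 42% vs 38.5%; this barely changes the information fractions below.

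**2. Information at the interim.** All GPs recruit in parallel, so the between-GP part of the variance does not shrink as patients accrue. The information fraction t = V(50)/V(m) therefore exceeds the fraction of patients:

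- a quarter of each GP's patients (m = 12.5): V = 0.05117, t = 0.44
- half (m = 25): V = 0.03200, t = 0.70

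**3. Chance that a true design effect is non-significant at the interim.** P = 1 − Φ(θ√t − 1.96), with θ = 1.96 + z(power) = 2.80 or 3.24. Power left if the rule binds is the probability of significance at both looks, from a bivariate normal with correlation √t.

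| Patients in, per GP | t | P(non-significant), 80% / 90% design | Power left, 80% / 90% design |
|---|---|---|---|
| a quarter | 0.44 | 54% / 43% | 44% / 56% |
| half | 0.70 | 35% / 23% | 63% / 76% |
| nearly all | 0.9 to 1.0 | 24–20% / 13–10% | tends to 80% / 90% |

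Example: a quarter in, 90% design: 3.24 × 0.662 − 1.96 = 0.186, and 1 − Φ(0.186) = 43%.

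**4. Calendar.** With a common start and uniform accrual over T months, 3-month data on a fraction f of patients exist at month 3 + fT, when min[1, (3 + fT)/T] are enrolled. For T = 6:

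| f with 3-month data | Month | Enrolled |
|---|---|---|
| 25% | 4.5 | 75% |
| 50% | 6.0 | 100% |
| 100% | 9.0 | 100% |

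With T = 3.8 months, only (3.84 − 3)/3.84 = 22% have 3-month data when enrolment closes. A look at calendar month 3 would find 50% (T = 6) to 78% (T = 3.84) enrolled and essentially no 3-month data.

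**The case against.** The second half of the rule refers to the end of full follow-up, so futility was probably the intent. That is fair, but intent does not remove the *or*. An analysis plan that ignored interim non-significance would contradict the protocol rather than complete it.

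The power loss and the late timing do not bite fully together. Index-visit tests are on forms sent in weekly, so a look that waits for all patients would have nearly full information on tests, and the loss would shrink to the design's own type II error. This stands, and is why the loss is given as a range.

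A reader might make three stronger inferences, none of which is supported:

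- *That the rules as written inflate the false-positive rate.* Two unadjusted 5% looks would give 8.3% at half the information, but only if the non-significance stop is ignored. If it binds, a false positive needs a significant interim, so the error for one endpoint cannot exceed 5%. The harm is to power. The missing efficacy boundary alone is something an analysis plan may hold.
- *That the loss is 71% or 63% at a quarter and 49% or 37% at half.* Those figures apply to information fractions of 0.25 and 0.5. If the fractions are of patients, clustering raises the information and the figures in the working apply.
- *That every patient has had the score applied before the interim, so that stopping can protect nobody.* Only intervention-arm patients have it applied, 3-month calls come in on a rolling basis, and no passage says that the analysis waits for everyone. The data cut is unstated, not fixed at month 9.

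**Conclusion.** The concern holds for the rule that section 3.4 fixes. Taken as written, interim non-significance would stop a trial with a true design effect on tests about half the time with a quarter of each GP's patients in (54% or 43%) and about a quarter to a third of the time with half in (23% or 35%). These figures rest on a two-sided 5% test, the assumed effect, a coefficient of variation of 0.2 and parallel recruitment by all GPs; they fall towards 20% or 10% for a late look. With no endpoint named, the rule could also fire on outcomes where no difference is hoped for.

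The timing problem holds in a limited form. Sections 3.1, 3.4, 8.2 and 10.1, read together with a common start and uniform accrual, put half of the 3-month data at the close of enrolment and all of it three months later. By then the stopping actions described could no longer affect any enrolled patient's assessment. The passages need reconciling.

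**What to change.** In section 3.4, delete interim non-significance as a stopping trigger. Keep only the futility clause (no reasonable prospect of a difference at the end of complete follow-up), make it non-binding, and restrict it to extra investigations, the variable that sized the trial. This is a wording change with no extra patients or contacts, and it preserves the design power.

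Reconcile sections 3.1, 3.4, 8.2 and 10.1 by stating an interim data cut that falls before enrolment closes. One example is a quarter of patients (3,750) at 3 months: about month 4.5 under 6-month accrual, with about 25% not yet enrolled. At the fastest accrual (3.8 months) even this cut falls after enrolment closes (month 3.96), so the cut should be tied to the observed rate.

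The cost is a less precise interim that can show only large safety differences. As an illustration, apply the cluster formula with 12.5 patients per GP, one-sided 2.5%, 80% power and assumed 3-month event rates of 8% down to 2%: the smallest detectable risk ratios are about 1.3 to 1.8. With 1,500 patients (5 per GP) they are about 1.6 to 2.3.

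Any efficacy boundary, conditional-power threshold or safety threshold is for the sponsor to choose.
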